1.2 SCHEMA

A graphical representation of study design is shown in [Figure 2](#):

Figure 2 - Graphical study design

Abbreviations: C1 = Cycle 1; C2 = Cycle 2; D1 = Day 1; DL = dose level; DLT = dose-limiting toxicity; EOT = end of treatment; ICF = informed consent form; IMP = investigational medicinal product; Q2W = every 2 weeks.

1.3 SCHEDULE OF ACTIVITIES (SOA)

1.3.1 Study flow chart

	Pre-screening ^a	Screening ^b	Treatment Cycle 1		Treatment Cycle 2 and thereafter		End of treatment	90 (±7) day (3 month) Follow-up ^d	Notes
Day		Days to first infusion	D1		14 (±2) days from previous infusion		30 (±5) days from last infusion		
			Pre-infusion ^c	EOI	Pre-infusion ^c	Every 6 weeks (±7 days)			
CEACAM5 expression status ^a (archival or fresh tumor tissue) - central IHC/prescreening Informed consent	X								
Informed Consent		X							
Inclusion/exclusion criteria		≤28	X						Section 5.1, Section 5.2
Demography, medical/surgical/disease history ^e		≤28							
Tumor characteristics ^f	X	≤28							
Height		≤7							
Performance status (ECOG)		≤7	X		X		X	X	Section 8.2.1, Section 8.2.3
Physical examination, including vital signs, body weight ^g		≤7	X		X		X	X	Section 8.2.1
Hematology ^h		≤7	X		X		X		Section 8.2.6, Section 10.2 (Appendix 2)
Coagulation ⁱ		≤7	X		X		X		Section 10.2 (Appendix 2)
Clinical blood chemistry ^j		≤7	X		X		X		Section 8.2.6, Section 10.2 (Appendix 2)
Urinalysis ^k		≤7	X		X				Section 10.2 (Appendix 2)

	Pre-screening ^a	Screening ^b	Treatment Cycle 1		Treatment Cycle 2 and thereafter		End of treatment	90 (±7) day (3 month) Follow-up ^d	Notes	
Day		Days to first infusion	D1		14 (±2) days from previous infusion		30 (±5) days from last infusion			
			Pre-infusion ^c	EOI	Pre-infusion ^c	Every 6 weeks (±7 days)				
HBsAg & HCV serology and HIV test (only if required at country level)		X								
Urine/serum pregnancy test ^l		≤7			X		X	X	Section 8.2.8; Section 10.2 (Appendix 2)	
Left ventricular ejection fraction (MUGA/echocardiogram) ^m		≤28							Section 8.2.5	
12-lead ECG ⁿ		≤7	X	X	X		X		Section 8.2.4	
Specific ocular tests ^o		≤28					X		Section 8.2.2	
Assessment of ocular/visual symptoms			X		X				Section 8.2.2	
Tusamitamab ravtansine/Ramucirumab administration			X		X				Section 6.1	
AE assessment ^p	X	Continuously throughout the study period								
Concomitant medication ^q		X	Continuously throughout the study period							Section 6.8
Tumor assessment – RECIST 1.1 - CT/MRI ^r		≤28				X	X	X	Section 8.1, Section 10.13 (Appendix 13)	
Circulating CEA ^s	X	≤28				X	X	X	Section 8.6	
Plasma and whole blood for future analysis (optional) ^t			X						Section 8.6	
IgG			X							
Record further anticancer therapy								X		
Tusamitamab ravtansine and ramucirumab PK			Refer to PK/ATA flowchart, Section 1.3.2							Section 8.4
Tusamitamab ravtansine immunogenicity			Refer to PK/ATA flowchart, Section 1.3.2							Section 8.7

Abbreviations: AE = adverse event; AESI = AE of special interest; ALP = alkaline phosphatase; ALT (SGPT) = alanine aminotransferase; aPTT = activated partial thromboplastin time; AST (SGOT) = aspartate aminotransferase; ATA = antitherapeutic antibody; BUN = blood urea nitrogen; CEA = carcinoembryonic antigen; CEACAM5 = carcinoembryonic antigen-related cell adhesion molecule 5; CR = complete response; CT = computed tomography; eCRF = electronic case report form; ECOG = Eastern Cooperative Oncology Group (performance status); ECG = electrocardiogram; eGFR = estimated glomerular filtration rate; EOI = end of infusion; HBsAg = hepatitis B virus surface antigen; HCV = hepatitis C virus; HIV = human immunodeficiency virus; IgG = immunoglobulin G; IHC = immunohistochemistry; IMP = investigational

medicinal product; INR = International Normalized Ratio; LDH = lactate dehydrogenase; LVEF = left ventricular ejection fraction; MRI = magnetic resonance imaging; MUGA = multigated acquisition scan; PD = progressive disease; PD-L1 = programmed death ligand 1; PK = pharmacokinetic; PR = partial response; RBC = red blood cells; RECIST = Response Evaluation Criteria in Solid Tumors; SAE = serious AE; SD = stable disease; WBC = white blood cells.

- a **Prescreening:** a prescreening Informed Consent will be signed by the participant for CEACAM5 assay on archival or fresh tumor tissue and circulating CEA assay.
- b **Screening:** Informed consent should be signed before any study-specific procedures. It can be signed more than 28 days prior to initiating study treatment. Screening time indicates the time frame in which exams used to support eligibility must be done prior to initiating therapy. All tests or procedures on D1 should be done at predose time unless otherwise stated. Assessments must be performed prior to first IMP administration: participants must have confirmed CEACAM5 expression as assessed centrally. Baseline evaluations should be completed within 1 week prior to initiation of therapy, except for tumor assessment, circulating CEA, echocardiography, and ocular tests that may be performed within 4 weeks prior to the first IMP administration. The Investigator should review results of these tests prior to initiating therapy.
- c **D1 predose:** Cycle 1 D1 refers to the day the participant receives the initial dose of IMP. D1 of Cycle 2 and of each subsequent cycle corresponds to D15 of the previous cycle. During treatment, D1 assessment can be done on the day of infusion (before infusion) or the day before. C1D1 hematology, blood chemistry, coagulation and urinalysis tests may be omitted if baseline test performed within 7 days are normal. If baseline tests are abnormal should be repeated within 2 days of first study intervention.
- d **Follow-up visit:** SAEs/AESIs (regardless of relationship with study treatment) and IMP-related AEs ongoing at the end of study treatment, and any new IMP-related AE/SAE/AESI will be followed until resolution or stabilization (defined as an event ongoing without any change for at least 3 months). Date of disease progression and further anticancer treatment will be collected at the follow-up visit. Participants who stopped treatment before documented progressive disease (PD; ie, achieving stable disease [SD] or complete or partial response [CR or PR]) should undergo a tumor assessment and an on-site follow-up visit every 8 weeks (± 7 days) after the last tumor assessment until radiological disease progression, death, cut-off date for secondary endpoints, initiation of further anticancer therapy, or withdrawal of the participant's consent, whichever comes first. Participants with documented disease progression should attend an on-site follow-up visit 90 days after the last dose of study medication. If every ongoing related AE/SAE/AESI is resolved or stabilized, no further follow-up visit is needed; otherwise an on-site follow-up visit will be performed every 12 weeks after the End of Treatment visit until resolution of the event.
- e **Disease history** includes previous antitumor therapy (type, start and end dates, reason for discontinuation and response to the therapy).
- f **Tumor characteristics:** data collected will include histologic types, stage at diagnosis, disease extent at study entry; known specific mutations (*BRAF*, *KRAS*, *NRAS*, *PIK3CA*, *PTEN*, *PTP53*, *CCDN1*, *NTRK1*, *NTRK2*, *NTRK3*), known HER2 and MET status (data collected at screening) and known PD-L1 expression (data to be collected only at prescreening).
- g **Physical examination** will include: vital signs (temperature, blood pressure, heart rate) and examination of major body systems. Signs and symptoms will be reported in the electronic case report form (eCRF) as AEs only if they are still present at the time of first IMP administration.
- h **Hematology:** Hemoglobin, hematocrit, RBC, WBC with differential, platelet counts. These tests will be done before IMP administration at each cycle. If Grade 4 neutropenia, assess absolute neutrophil count (ANC) every 2-3 days until $ANC \geq 0.5 \times 10^9/L$. During first 2 cycles, hematology will be performed weekly.
- i **Coagulation:** International normalized ratio (INR), activated partial thromboplastin time (aPTT).
- j **Clinical blood chemistry:** Liver function tests: AST (SGOT), ALT (SGPT), total bilirubin, conjugated bilirubin, ALP. Renal function tests: Urea (or BUN) & creatinine; eGFR. Electrolytes: Sodium, potassium, calcium, glucose, Others: LDH, albumin and total proteins. During first 2 cycles, liver function tests will be performed weekly. The liver function tests and renal function tests will be done before IMP administration at each cycle, unless clinically appropriate. In case of Grade ≥ 3 liver function test abnormal, additional tests will be repeated every 2-3 days until recovery to baseline value.
- k **Urinalysis** tests on morning spot will be performed by dipstick at baseline, and at every treatment cycle. In case of proteinuria $\geq ++$ (dipstick), proteinuria quantification by proteinuria/24 h should be performed. If proteinuria >500 mg/24 h: blood tests including haptoglobin, LDH, platelet count and schizocytes should be performed systematically.
- l **Serum pregnancy test:** women of child-bearing potential must have a negative serum pregnancy test result within 7 days prior to the initial dose of IMP. A pregnancy test (serum/urine) will be repeated every 4 weeks before IMP administration, and a serum test will be repeated at the End of Treatment evaluation (30 \pm 5 days after the last IMP administration), and at the Follow-up visit (90 \pm 7 days after last IMP dose).
- m **Echocardiogram or MUGA scan:** left ventricular ejection fraction (LVEF) will be evaluated during screening period, and whenever clinically indicated.
- n **12-lead ECG** is required at baseline before starting and after completing the first IMP administration (within 30 minutes after the end of tusamitamab ravtansine infusion); before IMP administration at each cycle; and at the End of Treatment evaluation, 30 (\pm 5) days after last IMP administration.
- o **Specific ocular tests** will include assessment of ocular/visual symptoms and ocular exams including visual acuity, slit lamp under dilatation, and Schirmer's test at screening and whenever clinically indicated.
- p **AE:** For participant who was prescreened and had fresh biopsy, only the AEs related to the fresh biopsy procedure itself should also be reported in eCRF as general requirement of AE/SAE with the reporting time frame interval of 1 month for the prescreening period after fresh biopsy
- q **Concomitant medication** will be recorded in the eCRF from 28 days prior to the first study intervention administration, before every cycle during the study treatment period, and for up to 30 days after the final dose of study intervention. Once the participant has withdrawn from study treatment, concomitant medication should only be recorded if used to treat new or unresolved study treatment-related AEs.
- r **Tumor assessment:** Chest, abdomen, pelvic CT scan or MRI and any other examinations as clinically indicated will be performed to assess disease status at baseline and then every 6 weeks (± 7 days) during the study treatment period until radiological disease progression; initiation of further anticancer therapy; death; or cut-off for secondary endpoints. The scheduled tumor assessment time point will not be modified in case of a cycle delay. Brain CT-scan or MRI should be performed at baseline only for known stable lesions or if clinically indicated and followed during treatment only for participants with brain lesions at baseline.

- s CEA samples should be collected before IMP infusion, and as close as possible to tumor assessment.
t Plasma and whole blood samples to be collected for future use before infusion on Day 1 or the day before (optional).

1.3.2 Pharmacokinetic/Antitherapeutic antibody flow chart for Part 1 and Part 2

Cycle		C1		C2	C3	C4		Subsequent cycles ^{b,c,d}	EOT	
Day		D1	D4	D1	D1	D1		D1	D30 ±5 days after last IMP	
Ramucirumab	IV infusion	X--	--X		X	X	X		X	
	Sample RNT (hours) Ref. ramucirumab SOI	SOI	EOI		SOI	SOI	SOI		SOI	
	Sample time window	(-24h, SOI)	± 10 min		(-24h, SOI)	(-24h, SOI)	(-24h, SOI)		(-24h, SOI)	
	PK sample ID	S00 ^a	S01		S00 ^a	S00 ^a	S00 ^a		S00 ^{a,b}	
Tusamitamab ravtansine	IV infusion	X--	--X		X	X	X		X	
	Sample RNT (hours) Ref. tusamitamab ravtansine SOI	SOI	EOI	72h	SOI	SOI	SOI	EOI+1h	SOI	
	Sample time window	(-24h, SOI)	± 10 min	± 24 h	(-24h, SOI)	(-24h, SOI)	(-24h, SOI)	± 10 min	(-24h, SOI)	
	PK sample ID	P00 ^a	P01	P02	P00 ^a	P00 ^a	P00 ^a	P01	P00 ^{a,c}	
	ATA sample ID	AB00 ^a			AB00 ^a	AB00 ^a			AB00 ^{a,d}	ABF00

Abbreviations: AB = antibody; ATA = antitherapeutic antibody; C = cycle; D = Day; EOI = End of infusion; EOT = End of -Treatment; F = final; IMP = investigational medicinal product; IV = intravenous; P = plasma; PK = pharmacokinetic; RNT = relative nominal time; S = serum; SOI = start of infusion.

- a Samples collected strictly before start of infusion (SOI), tusamitamab ravtansine and ramucirumab predose samples can be collected at the same time before ramucirumab administration.
b Ramucirumab PK samples will be collected at SOI at Cycle 7 only. After the cut-off date for the primary analysis, no more PK samples will be collected.
c Tusamitamab ravtansine PK samples will be collected at SOI each cycle at Cycles 5, 6 and 7 and thereafter at Cycle 13 only. After the cut-off date for the primary analysis, no more PK samples will be collected.
d Tusamitamab ravtansine ATA samples will be collected at SOI at Cycle 7 and thereafter every 6 cycles (ie, C7, C13, C19...).

Note: The sampling time-points for PK and ATA may be reduced during the course of the study based on the updated knowledge of drug behavior, upon notification from the Sponsor.

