- E 25. Washout period before the first administration of study intervention of less than 3 weeks or less than 5 times the half-life, whichever is shorter, for prior antitumor therapy (chemotherapy, targeted agents, immunotherapy and radiotherapy, or any investigational treatment).

- E 26. Poor coagulation as defined by International Normalized Ratio (INR) ≥ 1.5 or prothrombin time (PT) $\geq 1.5 \times$ upper limit of normal (ULN) and partial thromboplastin time/activated partial thromboplastin time (PTT/aPTT) $\geq 1.5 \times$ ULN, unless the participant is receiving anticoagulation therapy. Participants receiving warfarin must be switched to low-molecular-weight heparin and must achieve a stable coagulation profile prior to the first IMP administration.

Prior/concurrent clinical study experience

- E 27. Previous enrollment in this study, current participation in any other clinical study involving an investigational study treatment, or any other type of medical research.

Diagnostic assessments

- E 28. Poor organ function as defined by any one of the following prior to IMP administration:
- a) Serum creatinine $>1.5 \times$ ULN or estimated glomerular filtration rate (eGFR) <60 mL/min/1.73 m² as estimated using a Modification of Diet in Renal Disease (MDRD) formula.
 - b) Total bilirubin $>1.0 \times$ ULN (excluding congenital conjugation disorders [Gilberts], for whom total bilirubin $\leq 3.0 \times$ ULN, with direct bilirubin $\leq 1.5 \times$ ULN, is allowed).
or
aspartate aminotransferase (AST), alanine aminotransferase (ALT) $>2.5 \times$ ULN (In case of documented liver metastasis, AST, ALT $<5 \times$ ULN is allowed).
 - c) Neutrophils $<1.5 \times 10^9$ /L, platelet count $<100 \times 10^9$ /L, or hemoglobin <9 g/dL (blood infusion-free for at least 2 weeks).
- E 29. Urine dipstick or routine analysis indicating proteinuria of 2+ or higher, unless a 24 hour urine collection demonstrates <1000 mg of protein.

Other exclusions

- E 30. Accommodation in an institution because of regulatory or legal order (eg, prisoners or participants who are legally institutionalized).
- E 31. Any country-related specific regulation that would prevent the participant from entering the study - see Appendix 8 ([Section 10.8](#)) of the protocol (country-specific requirements).

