Any patient who has had 1 tusamitamab ravtansine dose reduction or 2 ramucirumab dose reductions and who experiences an event that would cause an additional dose reduction must be discontinued from tusamitamab ravtansine/ramucirumab.

If 1 of the 2 drugs (tusamitamab ravtansine or ramucirumab) is prematurely permanently discontinued, the other drug can be continued until disease progression.

Retreatment of a patient requiring a dose delay of more than 1 month will need to be justified by an individual case risk-benefit assessment.

6.5.1 Retreatment criteria: Part 1 and Part 2

All participants entered into the study will be treated at Day 1. A participant may receive additional study interventions if he/she meets retreatment criteria as determined by the Investigator and agrees to be retreated.

At Day 1, the participant must meet all of the following criteria to be eligible for retreatment:

- Neutrophil count $\geq 1.5 \times 10^9/L$.
- Platelets $\geq 100 \times 10^9/L$.
- Total bilirubin $\leq 1.5 \times ULN$.
- AST, ALT $\leq 2.5 \times ULN$ or $\leq 5 \times ULN$ in case of documented liver metastasis.
- No IMP-related toxicity Grade >1 (except for alopecia) or baseline severity.

- Urine protein:
 - <2+ on dipstick or urinalysis for C1D1
 - ≤2+ on dipstick or urinalysis for subsequent infusions
- OR
- <2 g on 24 hour urine collection.
- Hypertension is controlled. Every attempt should be made to control blood pressure (<150 mmHg systolic and <90 mmHg diastolic).
 - Wound healing: any wound is fully healed.

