6.8 CONCOMITANT THERAPY

Any medication or vaccine (including over-the-counter or prescription medicines, recreational drugs, vitamins, and/or herbal supplements) that the participant is receiving at the time of enrollment or receives during the study must be recorded along with:

- Reason for use
- Dates of administration including start and end dates

The Sponsor should be contacted if there are any questions regarding concomitant or prior therapy.

Participants must abstain from taking prescription or nonprescription drugs (including vitamins, recreational drugs, and dietary or herbal supplements) within 7 days (or 14 days if the drug is a potential enzyme inducer) or 5 half-lives (whichever is longer) before the start of study intervention until completion of the follow-up visit, unless, in the opinion of the Investigator and Sponsor, the medication will not interfere with the study.

Concomitant medication may be considered on a case-by-case basis by the Investigator, in accordance with the following guidelines:

- Participants with well controlled HIV infection must receive a stable ART regimen containing no antiretroviral medication other than the following: abacavir, dolutegravir, emtricitabine, lamivudine, raltegravir, rilpivirine, and/or tenofovir.
- Palliative radiotherapy may be given for control of pain (for palliative intent). If palliative radiotherapy is being considered, the Sponsor should be contacted for approval prior to initiating treatment, and prior to resuming therapy on the study.

The irradiated area should be as small as possible and should involve no more than 20% of the bone-marrow in any given 3 week period. In all such cases, the possibility of tumor progression should be ruled out by physical and radiological assessments of the tumor. The irradiated area cannot be used as a parameter for response assessment. If the only evaluable lesions are to be irradiated, the participant will stop the study intervention.

- Any background therapy taken by the participant for concomitant illnesses other than cancer (eg, HRT, statin, antihypertensive medication) is allowed.
- Supportive treatment as medically indicated for the participant's well-being may be prescribed at the Investigator's discretion. Every medication or treatment taken by the participant during the trial and the reason for its administration must be recorded on the eCRF.

The following treatments are not permitted during this study:

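### The flow chart lets the loading dose rest on a blood count up to 7 days old, with no exception for participants who had chemotherapy less than 21 days before

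*Protocol*

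**What the plan says.** **The waiver.** Hematology is scheduled before infusion on C1D1 in the Section 1.3.1 flow chart. Note c then relaxes this: "C1D1 hematology, blood chemistry, coagulation and urinalysis tests may be omitted if baseline test performed within 7 days are normal". It adds: "If baseline tests are abnormal should be repeated within 2 days of first study intervention". Neither sentence mentions prior chemotherapy.

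**Later doses.** For the treatment period, note c says: "During treatment, D1 assessment can be done on the day of infusion (before infusion) or the day before". Note h asks for hematology before dosing at each cycle and adds: "During first 2 cycles, hematology will be performed weekly".

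**Washout.** E25 in Section 5.2 excludes a participant with a "Washout period before the first administration of study intervention of less than 3 weeks or less than 5 times the half-life, whichever is shorter", and it names chemotherapy among the therapies covered. Section 6.8 has a general rule on drugs taken before study treatment: "within 7 days (or 14 days if the drug is a potential enzyme inducer) or 5 half-lives (whichever is longer". It can be set aside: "unless, in the opinion of the Investigator and Sponsor, the medication will not interfere with the study".

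**Other checks before the first dose.** The flow chart marks the eligibility criteria for review at C1D1 as well as at screening. E28 applies before dosing; its part c sets the limits for neutrophils, platelets and hemoglobin. E06 excludes unresolved toxicity from earlier treatment. Section 8.2.7.3 bars starting Cycle 1 with hemoglobin below 9.0 g/dL. Section 6.5.1 opens with "All participants entered into the study will be treated at Day 1"; the neutrophil and platelet limits that follow are retreatment criteria.

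**The concern.** Inclusion criterion I05 requires progression on or after first-line treatment with a platinum, a fluoropyrimidine or both, so earlier cytotoxic exposure is the norm here. A normal count shows that marrow suppression has not yet appeared. It does not show that suppression is not on its way, and a count taken soon after a cytotoxic dose is the one most likely to miss it.

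The safeguard is also weakest where the dose is highest. From Cycle 2 each 100 mg/m² dose is tied to a count from that day or the day before. The 170 mg/m² dose (150 mg/m² at dose level −1) may be given on a count a week old. The footnote to Table 7 rules out a reduction at Cycle 1, so the only choice is to give the dose or hold it, and the pre-dose count informs that choice. Table 2 lists hematologic cytopenias as a potential risk of the conjugate and names blood counts before each administration as part of the mitigation.

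At stake is the safety of a participant who receives a full cytotoxic loading dose while counts from the previous regimen are still falling.

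**Working it through.** The plan gives no figure of its own on this point. The check is interval arithmetic on its timing rules.

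**Inputs from the documents:** the count may be up to 7 days old (note c); E25 uses 21 days or five half-lives; Section 6.8 uses 7 days or five half-lives; counts are weekly in Cycles 1 and 2 (note h).

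**Assumptions:** the half-life t of the prior agent, and a nadir 7 to 21 days after the last cytotoxic dose. Neither is in the documents.

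**Step 1: shortest interval from chemotherapy to first dose.** E25 minimum = min(21, 5t). Section 6.8 minimum, if it is also applied and not waived = max(7, 5t). E25 falls below 21 days when t < 21/5 = 4.2 days. The 7-day floor in Section 6.8 matters when t < 7/5 = 1.4 days.

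| Assumed t (days) | E25 (days) | Section 6.8 (days) | Both (days) |
|---|---|---|---|
| 0.5 | 2.5 | 7 | 7 |
| 1.4 | 7 | 7 | 7 |
| 2 | 10 | 10 | 10 |
| 3 | 15 | 15 | 15 |
| 4 | 20 | 20 | 20 |
| 4.2 | 21 | 21 | 21 |

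**Step 2: how early the qualifying count can be.** Oldest allowed count, in days after the last cytotoxic dose = interval − 7. Assumed nadir relative to C1D1 = (7 to 21) − interval.

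| Interval (days) | Oldest count (day after chemotherapy) | Assumed nadir relative to C1D1 (days) |
|---|---|---|
| 7 | 0 | 0 to +14 |
| 10 | 3 | −3 to +11 |
| 14 | 7 | −7 to +7 |
| 20 | 13 | −13 to +1 |

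At 7 to 14 days, the oldest count falls no later than the start of the assumed nadir window, so it can be normal with the whole fall still to come. At 20 days it falls inside the window, and the window has nearly closed by C1D1. The concern therefore weakens as the interval lengthens.

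**Step 3: longest gap between planned counts.** With the waiver: 7 days before C1D1 plus 7 days to C1D8 = 14 days. With a C1D1 count: 7 days. If a repeat within 2 days were required of everyone, as it is after an abnormal baseline: 2 + 7 = 9 days.

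**Step 4: does another rule force a new sample?** The C1D1 eligibility review, E28 and the hemoglobin bar set conditions but give no sampling date closer than the 7 days that note c accepts. The count limits in Section 6.5.1 govern retreatment; its urine-protein line names C1D1, but its count lines do not. Note h sets the general rule and note c is the specific exception for C1D1. The same 7-day-old normal count can satisfy all of them.

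**The case against.** The strongest reply is that omission is an exception that needs several things at once. The count is scheduled by default, and note c only permits skipping it. The baseline must be normal, which is stricter than eligible, and an abnormal one must be repeated. Eligibility, including unresolved toxicity under E06, is reviewed again on the dosing day, and there is a physical examination. The investigator knows about recent chemotherapy and can order the count. The half-lives are assumed and tied to no named regimen, and a longer-lived component of a combination could bring the minimum back to 21 days. The clinical record is also reassuring: the monotherapy DLTs were keratopathy, and no Grade 4 event was reported among the 13 participants treated at 170 then 100 mg/m² (Sections 2.3.1 and 4.3).

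All of this stands as a limit on how often the problem would arise. None of it supplies a fresh count for a participant whose week-old result was normal.

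Three stronger readings are tempting, and the documents do not support them.

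- A reader might infer that eligibility is tested only at screening. The flow chart marks it again at C1D1; what is missing is a new sample.
- A reader might infer that the DLT assessment is compromised. The hematological DLTs in Table 6 are severe or complicated events, ordinary nadir neutropenia is not one, and the Study Committee confirms each DLT. An event wrongly blamed on the study drug would push towards a lower dose. Without a C1D1 count such an event would be harder to interpret, but this is secondary.
- A reader might infer that the SAP's baseline rule distorts the laboratory analysis. SAP Section 3.6.3.1 plans change from baseline for vital signs and ECG, and for hematology only grades at baseline and worst grades on treatment. A fall that began before dosing could count in the on-treatment grade, but no planned hematology change analysis is affected.

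**Conclusion.** The gap is real as a statement of what the protocol permits. A participant can receive the largest dose of a cytotoxic conjugate less than 21 days after chemotherapy, on a count up to 7 days old, with the next planned count about a week later. The measurable effect is a gap between counts of up to 14 days instead of 7. It matters most when chemotherapy ended about 7 to 14 days before C1D1.

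The sub-21-day window needs an assumed half-life under 4.2 days. The 7-day lower end needs Section 6.8 to apply alongside E25; on E25 alone the interval could be shorter. The nadir timing is assumed. The number of participants who start within 3 weeks of chemotherapy is unknown, so this is a permitted scenario and not an expected rate.

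A reader might also see an unresolved conflict between E25 and Section 6.8, since at an assumed 10-day half-life they give 21 and 50 days. E25 addresses prior antitumor therapy expressly and Section 6.8 is a general rule on medications, so the natural reading is that E25 governs. The point does not depend on settling this.

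Overall this is a modest safety clarification, between worth considering and a low-priority recommendation. It is worth making because it is cheap.

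**What to change.** Add one sentence to note c of the Section 1.3.1 flow chart: *C1D1 hematology may not be omitted if the last cytotoxic dose was within 28 days; the count is taken on the day of first infusion or the day before, and the E28c thresholds must be met before dosing.*

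The 28 days are the assumed 21-day nadir window plus the 7-day age allowed for the count: 21 + 7 = 28. From 28 days on, even the oldest allowed count falls on day 28 − 7 = 21 or later, at or past the end of that window. A team that assumes a different nadir should change the figure to match. The sentence works whichever washout rule governs and lengthens no washout.

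The cost is one blood count that is already scheduled by default, in recently treated participants only, and an occasional short dosing delay when the count fails E28c. If enrolment has closed, the change serves only later protocols that reuse this note.

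No ruling on precedence between E25 and Section 6.8 is needed for this point. A listing of DLTs beside time since chemotherapy would be optional and would change no result.
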